##### **Secondary Outcome Indicators**

1. Clinical consistency: Consistency between model-generated reports and physicians' final reports in terms of key conclusions;
2. Generalization ability: Stability of the model across different devices, disease types,

and populations;

3. Clinical efficiency indicators: Average model inference time, report generation speed, percentage reduction in physician review time;

4. Expert subjective ratings: Scale-based evaluation of the readability and clinical value of model-generated reports by physicians.

#### **Sample Size Estimation Process**

The sample size for the prospective validation of this study is determined based on statistical power analysis. Assuming the model achieves an accuracy of approximately 85% in the disease diagnosis task, compared with an 80% accuracy rate of manual diagnosis, with an expected detectable performance difference of 5%, a significance level ( $\alpha$ ) set at 0.05, and a test power ( $\beta$ ) set at 0.2, approximately 500–600 cases per group are required according to the binomial distribution sample size calculation formula, with a total of 1000–2000 newly enrolled cases needed to meet statistical significance requirements.

Considering potential loss to follow-up or data disqualification during the prospective study, the final plan is to collect complete multimodal data (including imaging, reports, and laboratory results) from approximately 2000 patients for model validation and performance analysis. This sample size ensures the accurate evaluation of the model's stability, generalization ability, and consistency with expert diagnosis in real-world clinical scenarios at a 95% confidence level.

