## **3. Research Design and Methods**

### **Prospective Validation of a Multimodal Imaging Large Model**

#### **(I) Study Design Type and Methodology**

This study is a single-center prospective observational study, aiming to conduct prospective validation and optimization of the established medical multimodal large model based on real-time collected clinical multimodal data (imaging, medical records, laboratory tests, reports, etc.). No additional interventions will be imposed on patients' diagnosis and treatment processes during the study; relevant data will only be collected synchronously during routine clinical examinations and diagnostic procedures, making it a non-interventional, minimal-risk prospective study.

During the study period, all newly diagnosed cases meeting the inclusion criteria will be consecutively enrolled. The research team will conduct prospective inference and performance validation of the multimodal medical large model based on imaging findings, EMR text, and laboratory test data, systematically evaluating the model's performance in tasks such as disease diagnosis, lesion localization, and report generation. Study results will be compared with clinicians' actual diagnostic conclusions and pathological gold standards to verify the model's generalization ability and clinical applicability in real-world scenarios.

The overall study protocol includes the following phases:

1. **Case recruitment and data collection:** Patients undergoing imaging examinations in the hospital will be consecutively recruited according to pre-defined inclusion criteria. Study data are derived from routine clinical workflows, covering imaging data, EMRs, laboratory results, and radiology reports. All data will undergo de-identification and quality control before being entered into the study database, with only the minimum necessary information retained.

2. **Model application and inference:** The research team will deploy the multimodal model in the hospital's secure computing environment. For each enrolled patient, the model will automatically generate disease predictions, lesion localization results, and diagnostic reports based on their imaging data and corresponding clinical text.

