#### **Statistical Analysis Procedures**

This study adopts intention-to-treat (ITT) analysis as the primary analytical strategy, conducting systematic statistical analysis on data from all enrolled cases. First, descriptive statistics are performed to summarize the baseline characteristics of patients, including age, gender, disease type, and imaging equipment source. Continuous variables are presented as mean  $\pm$  standard deviation or median depending on their distribution type, while categorical variables are expressed as frequencies. Inter-group differences are analyzed using appropriate statistical methods based on data characteristics: the t-test is used for normally distributed data, and the Mann–Whitney U test is used for non-normally distributed data.

In the analysis of primary outcome indicators, this study focuses on evaluating the model's performance in three core tasks: disease diagnosis, lesion localization, and report generation. For the disease diagnosis task, clinical final diagnosis or pathological results are used as the gold standard to calculate AUC, Sensitivity, Specificity, Accuracy, and F1-score, and receiver operating characteristic (ROC) curves are plotted to comprehensively assess the model's classification ability. For the lesion localization and segmentation task, expert annotations are used as references to calculate the Dice coefficient and Hausdorff distance, measuring the model's performance in lesion recognition range and boundary precision. For the report generation task, model-generated reports are compared with radiologists' reports at the text level, and natural language generation metrics such as BLEU, ROUGE, and CIDEr are used to evaluate language quality and semantic consistency.

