In the analysis of secondary outcome indicators, the overall benefits of the model are evaluated from the perspective of clinical usability. Clinical consistency is measured by physician double-blind ratings and Cohen's Kappa coefficient, assessing the consistency between model-generated reports and physicians' final reports in key diagnostic conclusions. Generalization ability is evaluated by stratifying and analyzing performance indicators across different disease types, devices, and populations to assess the model's stability in multiple scenarios. Clinical efficiency indicators are compared using the t-test or Mann–Whitney U test. Expert subjective ratings are obtained using a 5-point Likert scale, where radiology experts evaluate the readability,

clinical value, and ease of use of the model-generated reports.

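### The 85% versus 80% accuracy comparison is sized as two groups of 500–600, but the design is one paired cohort, the figure fails its own formula, and no named test addresses the comparison

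*Protocol*

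**What the plan says.** The sample size rests on one comparison. In Protocol section 3 (IV), Sample Size Estimation Process, the model is taken to be right in about 85% of cases. This is "compared with an 80% accuracy rate of manual diagnosis, with an expected detectable performance difference of 5" per cent. Alpha is 0.05 and beta is 0.2. A binomial formula is said to give 500–600 cases per group and 1000–2000 in total, and about 2000 patients are planned. Section 4, Prospective Study Phase, repeats this text.

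The design is described differently. Section 3 (I) sets out a single-centre observational study with no allocation. It states "For each enrolled patient, the model will automatically generate disease predictions", and says that results will be compared with clinicians' "actual diagnostic conclusions and pathological gold standards". Inclusion criterion 4 in section 3 (III) requires a radiology diagnostic report for every patient.

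Under Statistical Analysis Procedures, the primary diagnosis analysis calculates AUC, sensitivity, specificity, accuracy and F1-score for the model against the final clinical diagnosis or pathology. On tests, the section says "Inter-group differences are analyzed using appropriate statistical methods based on data characteristics" and then names the t-test and the Mann–Whitney U test. For secondary outcomes it adds Cohen's kappa for agreement on key conclusions, and says "Clinical efficiency indicators are compared using the t-test" or Mann–Whitney U.

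**The concern.** Whether the model is correct and whether the clinician is correct are two binary outcomes on the same patient. Their difference has a variance that depends on how often the two disagree in correctness (the discordance rate), and a two-group formula ignores this. A per-group number therefore describes a study other than the one designed.

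The comparison that justifies enrolment also has no counterpart in the analysis section. Manual accuracy is not estimated there, and no difference is tested. If the form of this comparison is settled only after the data are seen, its result cannot be presented as pre-specified.

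**Working it through.** **Inputs from the protocol:** model accuracy 0.85, manual accuracy 0.80, difference d = 0.05, alpha 0.05 (sidedness not stated, so both are tried), beta 0.2 (read as 80% power). **Assumed:** the discordance rate ψ, which the protocol does not give.

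**1. The plan's own figure.** For two independent groups,

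n per group = [z_α·√(2p̄q̄) + z_β·√(p₁q₁ + p₂q₂)]² / d²

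with p̄ = 0.825, so 2p̄q̄ = 0.28875 (root 0.5374), and p₁q₁ + p₂q₂ = 0.1275 + 0.16 = 0.2875 (root 0.5362).

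- Two-sided: (1.0532 + 0.4513)² / 0.0025 = 2.2635 / 0.0025 = 905.4, so 906.
- One-sided: (0.8839 + 0.4513)² / 0.0025 = 713.1, so 714.
- With a continuity correction: 945 and 753. Unpooled or arcsine versions: 903 and 711.
- A one-sample test of 85% against a fixed 80%: 471 two-sided, 368 one-sided.

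None of these falls in 500–600.

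**2. Power of the stated figure as a two-group test (two-sided).** Power = Φ[(0.05√n − 1.0532) / 0.5362].

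- n = 500: Φ(0.121) = 54.8%.
- n = 600: Φ(0.320) = 62.6%.

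One-sided, the power is 66.9% to 73.8%.

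**3. The paired calculation that fits the design.** With McNemar's test,

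N = [1.960·√ψ + 0.8416·√(ψ − d²)]² / d²

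where N is the total number of patients, each with both diagnoses. The margins bound ψ. It cannot be below 0.05 (the difference itself) or above 0.15 + 0.20 = 0.35. If model and clinician errors are unrelated, ψ = 0.85 × 0.20 + 0.15 × 0.80 = 0.29.

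| Discordance ψ | Patients for 80% power | Power with 2000 |
|---|---|---|
| 0.10 | 312 | >99.9% |
| 0.15 | 469 | >99.9% |
| 0.20 | 626 | 99.9% |
| 0.29 | 909 | 98.6% |
| 0.35 | 1097 | 96.6% |

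Worked example at ψ = 0.15: (0.7591 + 0.3232)² / 0.0025 = 468.6, so 469.

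A paired total of 500–600 arises only for ψ of about 0.16–0.19. The protocol states no such value and presents the number as a per-group one.

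**4. Does the planned enrolment suffice?** Yes, under either reading. Two groups of 906 make 1812. The largest paired requirement is 1097, so (2000 − 1097) / 2000 = 45% of patients could be lost before paired power fell below 80%.

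**5. Named tests against the comparison.** The t-test and Mann–Whitney U are listed for continuous data, split by normality. Kappa measures agreement on report conclusions. None of them tests a difference between two paired proportions.

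**The case against.** The strongest reply is that nothing material is lost. About 2000 patients exceed the requirement under either method. Even an unpaired analysis of 2000 patients would have at least 97.8% power at any possible discordance. This stands, and it limits the point to a wrong stated size and a mis-specified comparison.

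Second, the choice of test is commonly left to the SAP, which is not shown, and the protocol's wording about suitable methods is generic. This also stands in part: the absence of a valid test can be claimed only for this protocol. It does not excuse the per-group sizing, which the protocol states outright and which conflicts with its own design section.

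Three stronger readings are tempting, and the protocol does not support them:

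- *The study is underpowered.* The shortfall belongs to the 500–600 figure, not to the planned enrolment.
- *The accuracy comparison will be analysed with the t-test or Mann–Whitney U and so get wrong error bars.* The sentence naming those tests closes the paragraph on baseline description and is not tied to model-versus-manual accuracy.
- *The efficiency measures are also paired and wrongly tested.* The protocol does not say whether review times with and without the model come from the same cases. With different cases or a historical baseline, independent-sample tests would be correct.

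A further objection is that McNemar's test alone is not enough. The reference may be the final clinical diagnosis, which may include the clinician's own read. Manual accuracy would then be judged partly against itself, to the model's disadvantage. This is right, and the fix must cover it.

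**Conclusion.** The point holds in a limited form. The protocol sizes a paired, single-cohort comparison as two independent groups. Its 500–600 per group does not follow from its own inputs: 906 two-sided or 714 one-sided are needed, and the stated number gives about 55–63% two-sided power. No analysis in the protocol matches the hypothesis that justifies enrolment.

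It should be fixed, but it does not threaten the adequacy of the sample. The conclusion assumes that beta = 0.2 means 80% power, that the true accuracies are 85% and 80%, and, for the paired sizes, a discordance rate anywhere within the limits those accuracies allow. The two-group recalculation needs no assumption about discordance.

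**What to change.** In section 3 (IV) and section 4:

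- Replace the per-group statement with one cohort in which each patient has both diagnoses.
- State the comparison as the paired difference in accuracy (model minus manual, same patients, same reference), tested by McNemar's test with a paired 95% confidence interval.
- State the sidedness of alpha, and restate the requirement over an assumed discordance range: 312, 469, 626, 909 and 1097 patients at 10%, 15%, 20%, 29% and 35%. Note that about 2000 patients cover all of it.

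In Statistical Analysis Procedures:

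- Define manual diagnosis as the routine radiology report already collected, and keep it separate from the reference standard. A sensitivity analysis restricted to pathology-confirmed cases would show how much any overlap matters.
- Say whether efficiency times with and without the model come from the same cases. If so, use a paired t-test or the Wilcoxon signed-rank test; if not, the tests named can stay.

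The cost is protocol and SAP wording plus one extra analysis of data already planned. No added enrolment is needed.

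### The stated 500–600 cases per group do not follow from 85% vs 80% accuracy, alpha 0.05 and beta 0.2; the two-group formula needs about 906 per group

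*Protocol*

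**What the plan says.** The Protocol, section 3 (IV), Sample Size Estimation Process, puts the model's accuracy at about 85% and that of manual diagnosis at 80%, so the difference to detect is 5 points. Alpha is 0.05. Beta is 0.2, although the sentence calls it the test power. Sidedness is not given. From this it concludes that "approximately 500–600 cases per group are required according to the binomial distribution sample size calculation formula". It puts the overall need at 1000–2000 new cases.

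The next paragraph allows for loss or disqualified data, without a rate, and sets the final plan at about 2000 patients with complete multimodal data. Section 4, Prospective Study Phase, repeats both paragraphs word for word. No other power calculation appears in the Protocol.

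**The concern.** The text gives both accuracies, alpha, beta and the type of formula, so the figure can be checked directly. A 5-point difference between proportions near 80% usually needs far more than 500–600 per group at 80% power.

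The total does not follow either. Twice 500–600 is 1000–1200, yet the sentence gives 1000–2000, and the loss allowance comes only afterwards.

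At stake is whether the only sample-size justification can be relied on, and how much reserve the 2000 really contains. Against a need of 1000–1200 the reserve looks large. Against the correct two-group figure it is small.

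**Working it through.** **Inputs**, all from section 3 (IV): p1 = 0.85, p2 = 0.80, difference 0.05, alpha 0.05, power 0.80 (beta 0.2). Equal groups are assumed. Sidedness is not stated, so both cases are shown.

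**Attempt to reproduce 500–600 per group**

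Pooled two-proportion formula, with p̄ = 0.825:

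n = [z_α·√(2·p̄·(1−p̄)) + z_β·√(p1(1−p1) + p2(1−p2))]² / 0.05²

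- The two roots are √(2 × 0.825 × 0.175) = 0.5374 and √(0.1275 + 0.1600) = 0.5362.
- Two-sided: (1.960 × 0.5374 + 0.8416 × 0.5362)² / 0.0025 = (1.0532 + 0.4513)² / 0.0025 = 905.4, so 906 per group and 1,812 in total.
- One-sided: (1.645 × 0.5374 + 0.4513)² / 0.0025 = 713.0, so 714 per group.

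| Two-group version | Two-sided | One-sided |
|---|---|---|
| Pooled | 906 | 714 |
| Unpooled | 903 | 711 |
| Arcsine | 903 | 711 |
| Continuity-corrected | 945 | 753 |

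No two-group version reaches 500–600.

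**Power at the stated size**

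Power = Φ[(0.05·√n − z_α × 0.5374) / 0.5362]

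| n per group | Two-sided | One-sided |
|---|---|---|
| 500 | 54.8% | 66.9% |
| 600 | 62.5% | 73.8% |
| 1000 | 83.8% | 90.3% |

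Read as two groups of 1000, the plan of 2000 has about 84% two-sided power. The spare is (2000 − 1,812) / 2000 = 9.4%.

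**Other formulas that come near 500–600**

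- One-sample test against a fixed 80%, two-sided: 471, or 503 using only the variance at 80%. That design has one group.
- Paired (McNemar) test, two-sided, with discordance d: n = [1.960·√d + 0.8416·√(d − 0.05²)]² / 0.05². The Protocol states no d, so a range is needed. Independent errors give d = 0.85 × 0.20 + 0.80 × 0.15 = 0.29. The largest value these accuracies allow is d = 0.15 + 0.20 = 0.35.

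| Discordance | Patients for 80% power | Power at 1000 patients |
|---|---|---|
| 16% | 500 | 98% |
| 19% | 595 | 95% |
| 29% | 909 | 84% |
| 35% | 1,097 | 76% |

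At 2000 patients and d = 0.35, power = Φ[(0.05·√2000 − 1.960·√0.35) / √0.3475] = Φ(1.83), about 96.6%. Lower discordance gives more.

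A McNemar test thus yields 500–600 only at about 16–19% discordance, and then as a number of patients. It would not be a figure per group to be doubled to 1000 or more.

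**The case against.** The strongest reply is that the error does little harm in this study. Section 3 (I) describes one consecutive cohort in which the model runs on every enrolled patient and its results are compared with the clinicians' diagnoses. There are no two arms. A reader might infer that stopping at the lower end, 1000 cases, would leave about 55% power. The documents do not support that. In this design 1000 patients are about 1000 pairs, with 76% power at the maximum discordance, 84% under independent errors and 95% at 19%. Nor does any passage permit stopping at 1000: both sections fix the final plan at about 2000 patients with complete data. This objection stands and limits the consequence.

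It does not rescue the derivation. The text itself speaks of groups and reaches a total of at least 1000, which is two-group reasoning, and no paired or discordance assumption is stated. Unstated sidedness does not help either, since one-sided still needs 714.

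Calling beta the test power is a labelling slip, since the symbol and value make the meaning clear. The claim "This sample size ensures the accurate evaluation of the model's stability, generalization ability" has no calculation beside it, but the Protocol gives no stratum sizes and the detail may belong to an analysis plan not at hand. Neither point carries the finding.

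**Conclusion.** The point holds in a narrow form. Neither 500–600 per group nor 1000 as the lower end of the total follows from the stated inputs. The two-group requirement is 906 per group two-sided. The stated figure is therefore about 34–45% too low (1 − 600/906 = 34%; 1 − 500/906 = 45%). Two independent groups of the stated size would have 55–63% two-sided power instead of 80%. These figures assume equal groups and a two-sided test.

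The conclusion does not extend to the study being underpowered. About 2000 patients suffice under either reading: about 84% power as two independent groups of 1000, with about 9% spare, or at least 96% as pairs across the whole possible range of discordance. This is a wrong derivation of an adequate target. It should be fixed, but it does not endanger the study.

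**What to change.** In section 3 (IV), Sample Size Estimation Process, and section 4, Prospective Study Phase:

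- Delete the 500–600 per-group figure and the 1000–2000 total.
- Write power 0.80 (beta 0.20) and state the sidedness.
- Preferably, give a paired (McNemar) calculation with a stated discordance, because model and clinicians are assessed on the same patients. Show the range: about 500 patients at 16%, 909 at 29%, 1,097 at 35%, and at least about 96% power at 2000.
- If the two-group formula is kept, state 906 per group (1,812 in total) and that 2000 evaluable cases give about 84% power. Give the expected loss rate as well, since only about 9% is spare on that reading.

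The cost is wording in two places. Enrolment, endpoints and design do not change.

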#### **Statistical Analysis Procedures**

This study adopts intention-to-treat (ITT) analysis as the primary analytical strategy, conducting systematic statistical analysis on data from all enrolled cases. First, descriptive statistics are performed to summarize the baseline characteristics of patients, including age, gender, disease type, and imaging equipment source. Continuous variables are presented as mean  $\pm$  standard deviation or median depending on their distribution type, while categorical variables are expressed as frequencies. Inter-group differences are analyzed using appropriate statistical methods based on data characteristics: the t-test is used for normally distributed data, and the Mann–Whitney U test is used for non-normally distributed data.

In the analysis of primary outcome indicators, this study focuses on evaluating the model's performance in three core tasks: disease diagnosis, lesion localization, and report generation. For the disease diagnosis task, clinical final diagnosis or pathological results are used as the gold standard to calculate AUC, Sensitivity, Specificity, Accuracy, and F1-score, and receiver operating characteristic (ROC) curves are plotted to comprehensively assess the model's classification ability. For the lesion localization and segmentation task, expert annotations are used as references to calculate the Dice coefficient and Hausdorff distance, measuring the model's performance in lesion recognition range and boundary precision. For the report generation task, model-generated reports are compared with radiologists' reports at the text level, and natural language generation metrics such as BLEU, ROUGE, and CIDEr are used to evaluate language quality and semantic consistency.

In the analysis of secondary outcome indicators, the overall benefits of the model are evaluated from the perspective of clinical usability. Clinical consistency is measured by physician double-blind ratings and Cohen's Kappa coefficient, assessing the consistency between model-generated reports and physicians' final reports in key diagnostic conclusions. Generalization ability is evaluated by stratifying and analyzing performance indicators across different disease types, devices, and populations to assess the model's stability in multiple scenarios. Clinical efficiency indicators are compared using the t-test or Mann–Whitney U test. Expert subjective ratings are obtained using a 5-point Likert scale, where radiology experts evaluate the readability,

clinical value, and ease of use of the model-generated reports.

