3. **Clinical comparison and result documentation:** The model outputs will be subject to double-blind evaluation by radiologists and clinicians from relevant departments, compared with the final pathological or clinically confirmed results, and the accuracy, consistency, and interpretability of model predictions will be documented.

4. **Model iteration and continuous validation:** On the premise of ensuring ethical and privacy compliance, the research team will use newly collected data for continuous model fine-tuning and validation, analyzing its stability and robustness across different disease types, devices, and operational conditions.

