### **(3) Handling Measures**

Immediately discontinue the use of AI for the affected patient, initiate clinical remedial measures, and withdraw the patient from the study if necessary. SAEs must be reported via the hospital's internal Non-punitive Adverse Event and Near-miss Reporting System.

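### The diagnosis-task reference may be the clinicians' own final diagnosis, while the comparator, manual diagnosis, is never defined separately from it

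*Protocol*

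**What the plan says.** - **Reference.** Statistical Analysis Procedures: "clinical final diagnosis or pathological results are used as the gold standard to calculate AUC, Sensitivity, Specificity, Accuracy, and F1-score". Section 3 (I), phase 3, is equally open: model outputs are "compared with the final pathological or clinically confirmed results". Neither place ranks the two sources or provides for independent adjudication.
- **Comparator.** Section 3 (I): "Study results will be compared with clinicians' actual diagnostic conclusions and pathological gold standards". This sentence names only pathology as the gold standard, alongside the clinicians' conclusions.
- **Sizing.** Sample Size Estimation Process, repeated in Section 4: "Assuming the model achieves an accuracy of approximately 85% in the disease diagnosis task", "compared with an 80% accuracy rate of manual diagnosis". Manual diagnosis is not defined in either place.
- **Inclusion.** Section 3 (III) asks for complete imaging and a radiology report as the minimum data. It does not ask for pathology.
- **Model inputs.** Research Data Sources lists electronic record text that includes discharge summaries and surgical records.
- **Blinding.** The double-blind step in phase 3 covers the rating of model outputs, not the setting of the reference diagnosis.
- **Exposure to output.** Section 3 (I) calls the study non-interventional. Section 7 (1) gives anxiety after an AI misreading as an example of an adverse event, and Section 7 (3) says "Immediately discontinue the use of AI for the affected patient". A secondary outcome is the saving in physicians' review time.

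**The concern.** A reference that combines pathology with clinical confirmation can be acceptable when one test is described on its own. It is harder to defend when that test is compared with clinicians whose judgement helps to make the reference. In a patient without pathology, a wrong manual diagnosis that persists into the final diagnosis is scored as correct, and a model that was right is scored as wrong. This is incorporation bias, and it acts on the comparator.

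At stake is the 85% against 80% contrast on which the study is sized. If an unknown part of the observed difference comes from how the reference was set, the difference cannot be read as a difference in diagnostic accuracy.

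**Working it through.** **The plan's own figure.** The protocol gives 500–600 cases per group for 85% against 80%, alpha 0.05 and power 80%. The usual two-proportion formula with pooled variance under the null gives

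n = [1.960 × √(2 × 0.825 × 0.175) + 0.842 × √(0.80 × 0.20 + 0.85 × 0.15)]² / 0.05² = 906 per group (two-sided), or 714 one-sided.

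The stated figure is not reproduced. That is a separate matter, and nothing below depends on it. Only the accuracies 0.85 and 0.80 are carried forward.

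**Inputs for the bias**
- True accuracy 0.85 (model) and 0.80 (manual): Sample Size Estimation Process.
- f, share of patients whose reference is clinical only: not given, so assumed.
- g, share of manual errors in those patients that carry into the reference: not given, so assumed.
- Binary diagnosis, and model and manual errors independent: assumed.

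**Formulas.** Let x = f × g × 0.20, the proportion of all patients in whom a manual error becomes the reference.
- Apparent manual accuracy = 0.80 + x.
- Apparent model accuracy = 0.85 − 0.85x + 0.15x = 0.85 − 0.70x. Among these patients the model is truly right in 85% and is marked wrong; in the other 15% it shares the error and is marked right.
- Apparent difference = 0.05 − 1.70x.

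| f | g | x | Manual | Model | Difference (points) |
|---|---|---|---|---|---|
| 20% | 25% | 0.01 | 81.0% | 84.3% | +3.3 |
| 40% | 50% | 0.04 | 84.0% | 82.2% | −1.8 |
| 60% | 50% | 0.06 | 86.0% | 80.8% | −5.2 |

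The difference reaches zero at x = 0.05/1.70 = 0.0294, that is, at f × g = 0.147.

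**Sensitivity to the assumptions**
- *Correlated errors.* If every model error is also a manual error, the model is wrong in 0.15/0.20 = 75% of manual errors. Apparent model accuracy is then 0.85 − 0.25x + 0.75x = 0.85 + 0.50x. At f = 40% and g = 50% this gives 87.0% against 84.0%, or +3.0 points. The difference still shrinks but does not reverse.
- *More than two diagnoses.* If a wrong model diagnosis never matches the wrong reference, the 0.15x gain disappears and the difference is 0.05 − 1.85x. At x = 0.04 that is −2.4 points instead of −1.8.
- *Limiting case, by a cruder route.* Hold the model at 0.85 and let the manual diagnosis be identical to the clinical reference. Apparent manual accuracy is (1 − f) × 0.80 + f × 1.00, which equals 0.85 at f = 25%.

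**Patients needed in a pathology-confirmed stratum.** For a paired comparison (McNemar, two-sided 0.05, power 80%) with discordance ψ:

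n = [1.960√ψ + 0.842√(ψ − 0.05²)]² / 0.05².

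- ψ = 15%: 469 patients, 23% of 2000.
- ψ = 29%, the value under independence (0.85 × 0.20 + 0.15 × 0.80): 908.1, so 909 when rounded up, 45% of 2000.

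With 60% lacking pathology, 0.40 × 2000 = 800 patients remain. That is enough at 15% discordance but short of 909 at 29%.

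**The case against.** **Manual diagnosis may mean the radiology report.** Research Data Sources treats the radiology report as a source distinct from the rest of the record, so the reference could be a later and better-informed diagnosis. This is plausible, and it weakens the dependence. It does not remove it, since the report normally feeds the final diagnosis, and the protocol does not say which meaning applies.

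**No head-to-head test is specified.** The primary indicators and the analysis text describe the model against the reference. The comparison with clinicians comes from Section 3 (I) and the sample size text. That is correct, but it is still the contrast on which the study is sized.

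**The size is assumed.** Also correct: f, g, independence and the binary diagnosis are not in the protocol. The figures show what could happen, not what will.

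**Part of this may belong in the SAP.** A breakdown by reference type could be there. The choice of reference, however, is already fixed in the protocol in a form that lets it overlap with the comparator.

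A reader might infer three stronger things, which the protocol does not support:
- *Every disagreement is scored as a model error.* This holds only if the manual and reference diagnoses are identical, and in the scenarios above g is a quarter or a half.
- *The net bias runs against the model.* Incorporation of the manual diagnosis does push that way in these scenarios. But discharge summaries and surgical records may contain the reference diagnosis, and a model that reads them would be favoured.
- *Clinicians see the model's output, so the reference is contaminated.* Section 7 and the review-time outcome suggest use of the output, while Section 3 (I) describes a non-interventional study. The passages leave the matter open.

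**Conclusion.** The concern holds in a limited form. The protocol lets the comparator supply or feed the reference in patients without pathology, sets no bound on how many such patients there may be, and does not define manual diagnosis apart from the clinical final diagnosis. This inflates apparent manual accuracy and distorts the 85% against 80% contrast.

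With independent errors and a binary diagnosis, the true +5 points reads between +3.3 and −5.2 over the scenarios tabulated, and it vanishes once about 15% of manual errors across the whole study population carry into the reference (f × g = 0.147). With fully nested errors the middle scenario gives +3.0, so a change of sign is possible but not established. Because of what the model may read, neither the net direction nor the net size can be determined from the protocol.

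**What to change.** 1. **Statistical Analysis Procedures:** state that pathology is the reference whenever it exists and that the clinical final diagnosis is used only otherwise. Align Section 3 (I) with this.
2. **Sample Size Estimation Process and Section 4:** define manual diagnosis as the signed imaging report made before the reference diagnosis.
3. **Reporting:** give model accuracy, manual accuracy and their paired difference in all patients and separately by reference type. Read the pathology-confirmed stratum as the comparison free of this incorporation.
4. **Separately:** reconcile Section 3 (I), the review-time outcome, and Section 7 (1) and (3) on whether clinicians see model output before the manual and reference diagnoses are recorded. Which way to settle this is for the sponsor, since it concerns study conduct.

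**Cost.** Items 1 to 3 need changes of wording, plus the reference type and the date of the signed report recorded for each patient. No extra patients are required.

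**Downside.** The pathology-confirmed stratum over-represents biopsied or operated patients and has less power (469 patients needed at 15% discordance, 909 at 29%). It should therefore stand beside the all-patient result, not replace it. Among patients with a clinical reference, the earlier signed report reduces the dependence without removing it. The stratum also does not deal with records that reveal the reference to the model.
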